17.1 Is this study FDA-regulated?	
⊙ Yes ○ No	
17.2 Is this research funded wholly or in part by NIH?	
O Yes 🖸 No	
17.3 Is this study a Clinical Trial, as defined by FDA or NIH, and therefore needing registration on Clinical Trial help button to the right to learn more about the definition of a clinical trial.	als.gov? Click the
⊙ Yes ○ No	
17.5 Is the clinical trial already registered in ClinicalTrials.gov?	
 Not yet, but clinical trial will be registered prior to enrolling any subjects Yes No, this clinical trial will not be registered ClinicalTrials.gov #: 	
TBD	
Note: The following statement must be included verbatim in the consent form for trials that are/will be registered on ClinicalTrials.gov: "A description of this clinical trial will be available on http://www.ClinicalTrials.gov, as required by U.S. Law. This website will not include information that can identify you. At most, the website will include a summary of the results. You can search this website at any time."	
17.6 Who is responsible for registering this trial in ClinicalTrials.gov and ensuring information is updated, as a provide a name if the person is at Carilion or listed on the research team, or state the sponsor or lead site i lead site will register the trial.	
 The responsible party for an applicable clinical trial (ACT) must register the trial and submit results information. The responsible party is defined as: The sponsor of the clinical trial, as defined in 21 CFR 50.3; or The principal investigator (PI) of such clinical trial if so designated by a sponsor, grantee, contractor, or awardee, so long as the PI is responsible for conducting the trial, has access to and control over the data from the clinical trial, has the right to publish the results of the trial, and has the ability to meet all of the requirements for the submission of clinical trial information The responsible party for an ACT must submit the required clinical trial information no later than 21 days after enrollment of the first participant, but registration is highly recommended before enrollment begins due to some journal requirements. [name] 	
18.0 Study Procedures	
18.1 Provide a step-by-step description of the research procedures and/or and interactions with human subjects	s.

Provide a study schedule and list all activities or procedures that will be performed and describe the frequency and duration of research procedures, diagnostic and research

tests, questionnaires or surveys, specimen collection, and experiments, including screening, intervention, follow-up etc in step-by-step chronological order. State the length of time subjects will be in the study and the expected amount of time required for each study visit or activity. Describe how, when and where research activities will be administered and analyzed. If the research includes blinding, indicate whether researchers or subjects will be "unblinded" to study assignment and describe when and how this will be done.

- 1. For each study visit, participants will be asked to arrive 45 minutes before the beginning of their regularly scheduled follow-up visit. Research activities will take 45 minutes.
- 2. Upon early arrival to their regularly scheduled appointment, participants will be fitted for their very own, "athletic sleeve" by a member of the research team. This athletic sleeve will be used throughout the duration of the study. Patients will be asked to come wearing a tank top or short-sleeved t-shirt. If they do not come dressed as such, they will have the opportunity to change in a private space.
- **3.** Before donning the athletic sleeve, a member of the research team will measure the patient's upper limb circumference and induration and administer a baseline survey using the first section of the Lymphedema Life Impact Scale (LLIS document attached). Upper extremity circumference will be measured in centimeters at several points, which are: palmar crease, the wrist below the styloid process, wrist + 10 cm, wrist + 20 cm, wrist + 30 cm, and wrist + 40 cm. Upper extremity induration will be measured at the same points as circumference. These measurements are being taken solely for research purposes and should take approximately 3 minutes.
- 4. The athletic sleeve will be donned by the patient and the novel therapeutic device will be placed over it. A standardized sequence of vibratory therapy will be applied. The standardized sequence of vibratory therapy is as follows
 - This code goes through a series of 5 total phases for a 36 minute total treatment. The details of

each phase, and the total time spent in that phase are detailed below.

- Proximal Prep Phase (Total Time: 7 minutes) All proximal motors, 5-8, are on for the entire phase.
- Distal Prep Phase (Total Time: 7 minutes) All distal motors, 1-4, are on for the entire phase.
- Decongestion Phase (Total Time: 4 minutes) Moving proximal to distal, motor 8 to 1, the motors are turned on for 30 seconds then turned off before moving to the next motor pair.
- Clearing Phase (Total Time: 4 minutes) Moving distal to proximal, motor 1 to 8, the motors are turned on for 30 seconds then turned off before moving to the next motor pair.
- Reabsorption Phase (Total Time: 14 minutes) Moving distal to proximal, motors are turned on at different intensities mimicking a wave pattern.
- The pattern moves up the arm for 16 cycles. Use of this device will not impact standard of care in any way. The participant may ask to stop the research session at any time
- 5. The participant may ask to stop the research session at any timeThe athletic sleeve will then be removed, and a member of the research team will measure the patient's upper limb circumference and induration and administer a survey using the first section of the Lymphedema Life Impact Scale. These measurements are being taken solely for research purposes and should take approximately 3 minutes. Patients will be asked if they experienced any side effects or adverse effects.
- 6. Standardized decongestive therapy will be performed by qualified personnel. This step takes approximately 1 hour and would happen regardless or whether or not patients are enrolled in this study. The exact sequence and modality of therapy varies significantly from patient to patient, but a "typical" treatment session is as follows.

- Treatment today included:
- Manual Therapy provided for 30 minutes:
 - Large Vibration tool (https://www.rehab-store.com/p-magic-wandmassager.html) was applied at moderate pressure/compression on low setting x 3 minutes on each quadrant of the upper extremity covering anterior and posterior side of proximal arm and forearm to decrease pain, inflammation, and protein rich edema.
 - Large Vibration tool was then used to assist in lymphatic flow by using sweeping motion from distal to proximal on the upper extremity.
 - Small vibration tool (https://www.rehab-store.com/p-rolyan-minimassager.html) was applied to posterior side of the upper extremity in horizontal position and secured with a Coban wrap (https://fsastore.com /nexcare-no-hurt-self-adherent-wrap-3-in-x-80-in-tan/23594.html? gad_source=1&gclid=Cj0KCQiAnrOtBhDIARIsAFsSe51So6bK8D3doG ZZBzIxJLCcWTedkUUnBubn2Jr6nw7FyfTDwd9nGKcaAnMpEALw_wcB) at minimum pressure x 6 min to decrease protein rich edema and lymphatic stagnation in distal forearm.
 - After removal of Coban and small vibration tool, patient's forearm induration changed from moderate to mild.
 - Patient tolerated massage techniques of effleurage, petrissage, and cross friction to help alleviate pain, discomfort, muscle adhesions, and immobility to upper extremity and shoulder girdle area.
 - Myofascial release completed to pec, bicep, and deltoid to decrease fascial adhesions, decrease chronic inflammation, decrease pain, and increase range of motion.
 - Manual lymphatic drainage performed to abdomen, trunk, and upper extremity to increase lymphatic flow and decrease stagnation in tissues.
 - Manual Lymph Drainage performed to stimulate lymph nodes and lymphatic vessels to increase their activity and promote lymph flow using techniques of 3 seconds on/3 seconds off skin stretch and feathering toward inguinal lymph node group.
 - Patient tolerated active moving cupping techniques this date to lateral trunk to decrease fibrosis and edema.
 - NDT treatment techniques provided during manual treatment of placement and hold, loading and joint compression provided for postural alignment to increase upright posture to decrease pain while engaging in ADLs and IADLs.
- Therapeutic Activity provided for 30 minutes:
 - Therapist applied US to insertion of pec major to decrease adhesions and edema. US was applied at non thermal setting at 3 megahertz, 20% duty cycle and 1.5 output while patient was placed in active stretch x 7 minutes.
 - Patient instructed on stretching exercises of shoulder flexion and abduction.
 - Patient completed stretches with minimal assistance to maximize range of motion.
 - Patient instructed on each type of massage and pressure and sequence for each.
 - Patient educated on at home whole body exercises including light intensity cardio to increase strength and endurance.
 - Patient instructed on pain relief techniques of using massage and vibration tools to decrease pain. Patient's caregiver instructed on all types of massage and sequence and pressure for each to decrease pain.
- At the conclusion of the standardized decongestive therapy, the measurements and surveys conducted in step 3 will be repeated. Patients will also be asked if they experienced any side effects with the standard of care treatment.

8. This series of steps will be repeated at the patients' weekly follow-up visits for four weeks. Standardized decongestive therapy for lymphedema is most often performed on a weekly basis (and is one of the inclusion criteria for this study). Therefore, choosing this visit frequency would not greatly alter a patient's schedule or ability to perform other daily tasks. At the end of the four weeks, the patients will receive a \$20 Kroger gift card as compensation for their participation.	
9. If a patient chooses to withdraw from the study early or needs to be removed from the study for their own safety, notes will be added to research documentation and the patient' s Epic chart indicating their departure from the study. Going forward, they would receive standard decongestive therapy as before their participation in the study. They will receive a prorated compensation fee for their participation.	
10. Study subject limb circumference, induration data, and survey data will be analyzed using a paired t-test.	
You must attach surveys, instruments, interview questions, focus group questions, etc. in the Initial Submission Packet and label them clearly.	
18.2 Specify which procedures, tests, visits, etc. described above are part of usual standard of care at Carilion (are being performed solely for research purposes. If procedures, tests, visits are routinely performed for c are providing data for this research study, state this as well.	
Measurements of upper extremity circumference and induration along with assessment of pain level and presence /absence of side effects/adverse effects will be collected solely for research purposes. Use of the novel therapeutic device will also be done solely for research purposes. Standardized decongestive therapy is performed as part of the usual standard of care for lymphedema at Carilion Clinic. Patients would receive this if they were not part of this study. While decongestive therapy is routinely performed as part of clinical care, it is also producing data for this study, as we will be measuring upper extremity circumference and induration along with assessing the participant's pain level and experience of side effects after administration of this therapy.	
18.3 Describe the data collection methods and how data be compiled and collected for asses whether the data/specimens to be utilized in the repository are already in existence (re	

whether the data/specimens to be utilized in the repository are already in existence (retrospective) or if the data will be generated in the future (prospective).

- "Retrospective data" is data that is already in existence at the time of application receipt by the IRB. Retrospective is in reference to the date the data was GENERATED, not the date the data is COLLECTED. If all data is retrospective, please provide the start date from which data will be collected and the end date, and note that ALL data must be in existence at time of submission of this application.
 - Example: This IRB application is being submitted on 12/1/21 and is collecting data on a standard of care surgery and looking at patient outcomes. All surgeries for this retrospective studies will be completed between 11/31/2018 and 11/31/2021 (the day before the study is submitted to the IRB). This study will likely qualify for a waiver of consent.
- "Prospective data" includes any data (including data from the medical record) that are not currently in existence at the time of receipt of the application by the IRB, even if the data is being collected solely for Standard of Care. Prospective data collection typically requires informed consent from the participant to be able to use their clinical data or specimens for research purposes. If all data is prospective, please state date range from which data will be generated.
 - Example: This IRB application is being submitted on 12/1/21 and the study is collecting data on a standard of care surgery and looking at patient outcomes. All surgeries for this prospective studies will be completed between 1/1/2022 and 1/1/2025. This study will require informed consent UNLESS a waiver of consent is requested and justified.

Attach a copy of your data collection tool or spreadsheet listing exactly what data is to be gathered during this research study.

This research project will collect prospective data. The research team will collect the following specific measurements:

- Upper extremity circumference (measured in centimeters)
- Upper extremity induration
| • Lymphedema Life Impact Scale (LLIS - first section only) | |
|--|-----------------|
| • Any side effects or adverse effects experienced | |
| All measurements will be taken by designated study team members. | |
| Upper extremity circumference will be measured in centimeters at several points, which are: palmar crease, the wrist below the styloid process, wrist + 10 cm, wrist + 20 cm, wrist + 30 cm, and wrist + 40 cm. Upper extremity induration will be measured at the same points as circumference. | |
| Induration will be measured using a durometer (Rex Gauge Co. Model 1600 Dial Durometer Type OO) placed on the aforementioned points on the ventral surface of the proximal forearm. | |
| Lymphedema-related physical complaints will be measured using the first section of the Lymphedema Life
Impact Scale, a validated survey already widely used in the clinical care of lymphedema. | |
| Side effects and adverse effects are thoroughly detailed in section 23.1. Side effects include, but are not limited to, a skin tingling sensation, pain/soreness/swelling, dizziness, headache, nausea, and shortness of breath. | |
| These side effects will be recorded in the Data Collection Tool template inside the secure Carilion Clinic research environment. | |
| 18.4 Describe how long individual participants will be actively in the study. If there will be a period of time after
component of the study where participants will still be in the study (ex: participants outcomes are being ex
medical record at 1 year, but the last research study visit was at 3 months), state this as well. | |
| Patients will be actively participating in the study once a week, for four weeks. | |
| 18.5 Describe how long the entire study is expected to last, including data analysis. | |
| Patient recruitment for this study would take anywhere from 6 to 8 months. Each study participant will have 4 weeks of treatment, but each participant may not start at the exact same time, so study activities will take anywhere from 2 to 3 months. We will spend one month compiling and analyzing data. Altogether, this research project will take anywhere from 9 to 12 months. | |
| 18.6 Describe the qualifications of study personnel conducting the research procedures. This could include med specific to conducting the interventional procedures in this research, phlebotomy training for those drawin protocol specific training to be provided by the sponsor, or any other training to demonstrate that the rese are appropriately qualified to conduct the study. | ng blood, study |
| The specific interventional procedures involved in this research study include donning and doffing of the proprietary device, implementation of the proprietary device, measurement of limb circumference, and induration, and administration of the LLIS. The PI will ensure that all study team members have completed CITI training and are well-versed in the above procedures. | |
| Research team members will be trained on the use of the device by one of the inventors. Training will include the following benchmarks | |
| Putting the device on a study subject's arm and adjusting it so that it fits snugly Connecting the device to the external power bank and turning it on. Turning the device on is simple, and involves flicking a switch Carefully removing the device from a study subject's arm Safely storing the device in its designated space | |
| Research team members without a demonstrated conflict of interest are able to obtain measurements that result in the creation of data. [name], [name] (listed on this application), and [name] (VT collaborator) will train the entire research team on how to interact with patients and conduct study procedures that result in research data as well as document and report adverse events. This training will be logged and signed by one of the aforementioned trainers. | |
| 18.7 Please describe appropriate alternatives to the study procedures or course of treatment. | |

(For example: not to participate, standard of care treatment, other research study, same treatment offered off study)

At any point in time, patients may choose to opt out or not participate in the study. This will be made abundantly clear before any data is collected. If patients choose not to participate, they will only receive the standard of care for lymphedema, which is decongestive lymphatic drainage massage, and they will not receive treatment with the experimental device

Research Involving Device(s)

19.1 Device Name:

19.0

View Details	Device Name		Is the Device FDA Approved
Ξ	LymphaVibe		No
Manufacturer/ Device	Supplier of	VT BEAM	
Will Devices be Cost	e supplied at no	Yes	
Is the Device I	DA Approved	No	
Is an IDE nece	essary	No	

19.2 Describe any credentialing procedures and training in the use of the device that will occur prior to use.

Since the device (LymphaVibe) to be used in this research study is novel and proprietary, there is no official credentialing procedure.

[name], [name], [name] and [name] all played an important part in the development of this device from the ground up and know its operation inside and out. These individuals will formally train everyone else listed on this IRB in proper donning and doffing, operation, storage, maintenance, and troubleshooting of this device. Those that are trained on the use of this device will be maintained on a log in the Research Binder.

The below research team members may be trained on the device. This largely depends on individual research member schedules and how well individuals are able to cover research visits (i.e. less research team members may be trained if the need is not as great)

- [name] (PI)
- [name] (OT)
- [name] (medical student)
- [name] (research coordinator)
- [name] (undergraduate student)
- [name] (undergraduate student)

19.3 Who will assume primary responsibility for the storage of the device used in this study?

Name:

[name] and [name]

19.4 Describe storage and control of the device, including precautions being taken to minimize the chances of device use by health care providers not listed on this application.

(Ex: special ordering requirements, labeling, separate stocking, etc.).

The device will be stored securely, outside of the Carilion Clinic facility where research activities will be taking place as to avoid confusion between it and any other routinely utilized equipment. It will be brought in as needed for each patient and returned to its storage area afterwards. While in the clinic for study procedures, the device will be stored in a clear plastic tub that is labeled with the PI name, IRB number, and research study title. In addition to this information, the verbiage "Do NOT use as part of routine care. This device is for research activities ONLY" will be clearly written on the container. Providers at the aforementioned facility are aware of this research taking place and know that this device is investigational and currently for research use only.

Attach the PMA or cleared (510k) by FDA if used in accordance with labeling, or for investigational devices, attach sponsor/FDA risk assessment documentation if available in the Initial Submission Packet. Attach sponsor device manual of operations if available.

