Patients who have diagnosed lymphedema will be approached to participate in this study as part of their care. Patients will wear this device for approximately 40 minutes and then have certain measurements taken before and after doing so. These measurements include the size of their arm, how much pain/discomfort they are currently in, and if they experienced any side effects. After getting treatment with the device, they will receive the standard of care treatment for their lymphedema from their provider. After the standard of care has concluded, the previously mentioned measurements will be repeated. This data will be put together and analyzed to look for differences in arm size before and after treatment with the device as well as to look for the prevalence of side effects.

10.5 Provide background information about the research question(s.) Explain why the research is needed and include the relevance of this research to the contribution of this field of study.

Please include the current state of knowledge about your project topic by summarizing and synthesizing the available research (including published data) to provide justification for the study. Include a reference list of literature cited to support the protocol statement, either in your response below or as a supplemental document as part of the application packet.

Lymphedema is a chronic condition characterized by the buildup of protein-rich fluid in the body's tissues, leading to bothersome swelling. There are several causes of lymphedema, but it typically arises due to damage or dysfunction of the lymphatic system, which is composed of lymph drainage vessels and lymphatic fluid itself. Lymphatic drainage includes lymphatic capillaries, lymphatic trunks, and lymph nodes, creating one large lymphatic drainage network that is tightly controlled and highly associated with the circulatory system. Hydrostatic and oncotic forces push lymph out from the body's veins and arteries and into the body's tissues, where it is absorbed by lymphatic vessels and eventually recycled back into systemic circulation. Lymphatic fluid itself is very similar in composition to blood plasma, and it typically contains high levels of triglycerides, white blood cells, and bacterial debris. (Sleigh and Manna, 2022).

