Lymphedema can be subdivided into primary and secondary causes. Primary lymphedema is due to underlying genetic mutations, often leading to the malformation and malfunctioning of the lymphatic system. Secondary lymphedema is caused by some sort of external damage or injury to the lymphatic system. Most cases of lymphedema are secondary lymphedema, most widely seen in the oncologic population, where invasive surgery to remove tumors or diseased lymph nodes disrupts lymphatic flow. In fact, it is estimated that approximately 1 in 5 women who survive breast cancer will go on to develop lymphedema. While the underlying etiology of lymphedema may vary, all lymphedema is staged in the same fashion, falling anywhere from Stage 0 to Stage 3. Stage 0 represents an "at-risk" state, where an individual has risk factors associated with the development of lymphedema, and Stage 3 represents a stage of lymphostatic elephantiasis (Sleigh and Manna, 2022).

Lymphedema in and of itself can be uncomfortable, if not downright painful. However, it also predisposes patients to developing secondary vascular, inflammatory, and infectious conditions as it progresses and becomes increasingly severe. Additionally, it may undermine patients' body image and self-esteem and affect their daily lives and personal relationships. Currently, once lymphedema develops, there is no definitive cure, only symptom management. The standard of care entails using a combination of outpatient decongestive lymphedema therapy

and manual lymph drainage alongside stringent home care characterized by the use of compression garments and therapist-taught manual lymph drainage techniques. However, oftentimes home care is not enough to control lymphedema between therapist appointments.

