In recent years, medical devices have been developed to improve home care and lymphedema outcomes. There are many different types of lymphedema pumps currently available on the market. Unfortunately, across the board, they can be bulky, noisy, expensive, and require long periods of immobility while treatment takes place. There is a definitive need for new lymphedema technology that can improve patients' symptoms while being easier and more enjoyable to use than previous products. This study aims to evaluate a new, proprietary device designed at Virginia Tech through Carilion Innovations to address the problem of upper extremity lymphedema. A previously conducted safety study has demonstrated that this device does not cause significant changes in vital signs or pain. Additionally, the overwhelming majority of side effects associated with the use of this device are those expected with the standard of care. Being able to assess the efficacy and safety of this device in patients with lymphedema over the course of this study would provide a promising alternative to current lymphedema home care modalities that can improve lymphedema patient outcomes.

References:

10.6 State the research hypothesis or the question that the research will answer.

List the research objectives and expected outcomes. A primary outcome or objective must be identified. After the statement of the primary objective, secondary objectives may be listed. Objectives should be simple and specific.

Research Question: How can we utilize new technology in the treatment of lymphedema?

Hypothesis: Use of a recently developed, proprietary device will reduce lymphedema in the outpatient clinic setting.

Objectives:

- 1. Implement a new, proprietary device in the treatment of lymphedema.
- 2. Assess the safety and tolerability of the aforementioned device.
- **3.** Assess pre- and post-treatment pain metrics and change in upper extremity circumference and induration for treatment with the proprietary device and the standard of care.

10.7 State how qualitative and/or quantitative data will be analyzed in order to answer the research questions.

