For this study, a Data Safety and Monitoring Committee (DSMC) will be established. The committee consists of a physician, lymphedema therapist, and biomedical engineer. They will be familiar with the project, but will have no direct involvement in it. The DSMC will review any reports of anticipated side effects, unanticipated side effects, serious adverse events and unanticipated problems. The study population consists of 15 subjects. Routinely, after each of the first 2 cohorts of 5 study subjects each, the DSMC will conduct a review. The DSMC will only have access to de-identified data. Until this review is completed, and the DMSC makes a recommendation to continue, no subjects will be enrolled and studied. The DMSC will make its determinations based upon review of data that includes the incidence of side effects (physical risks and harms outlined in section 23.1) and incidence of adverse events and serious adverse events (outlined in section 23.2) For occurrence of any unanticipated side effects or adverse events, the study will be immediately suspended, and these conditions will be reviewed by the DSMC, followed by reporting to the IRB. The study will only continue if recommended by the DMSC and permitted by the IRB. Data that will be provided to the IRB if the Stop/Pause is activated will be submitted in writing, and include full disclosure of all data collected, and any written annotations associated with the study in the patient chart. A recommendation of whether the study should continue without modification, continue with modification, or no longer continue from the DSMC will be provided to the IRB in writing after each meeting is held.

23.7 Describe the plans and rationale for conducting an interim analysis.

🔿 Yes 💿 No

23.8 Have stopping rules been established for the study, including for reasons of futility?			
⊙ Yes ○ No			
Describe the stopping rules:			
If any of the following were to occur during the course of the research study, the study will be discontinued.			
 Bleeding or bruising Interference with electronic devices such as, but not limited to, hearing aids and mobile phones Any evidence of increasing edema with use of the device 			
23.9 Are there defined criteria (ex: rates of adverse events) for when study interventions should be discontinue	d?		
⊙ Yes ○ No			
Describe the criteria:			
If any of the following were to occur during the course of the research study, the study will be discontinued.			

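### Headache, dizziness, nausea and shortness of breath have no described pre-device check, and nothing says how a symptom present on arrival is classified

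*Combined protocol and SAP*

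**What the plan says.** Section 18.1 sets the order of events at each weekly visit.

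- Step 3, before the device: "Before donning the athletic sleeve, a member of the research team will measure the patient's upper limb circumference and induration", and the same person is to "administer a baseline survey using the first section of the Lymphedema Life Impact Scale". No other symptom enquiry is listed. Section 18.3 describes the survey's scope: "Lymphedema-related physical complaints will be measured using the first section" of the scale.
- Step 5, after the device: circumference, induration and the same survey section are repeated. Then comes a new item: "Patients will be asked if they experienced any side effects or adverse effects".
- Step 7, after standard decongestive therapy: the step 3 measurements and survey are repeated, and side effects of standard care are asked about separately.

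The lay description in 10.4 reads differently: "Patients will wear this device for approximately 40 minutes and then have certain measurements taken before and after doing so". The next sentence there names arm size, current pain or discomfort, and side effects as those measurements.

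Objective 2 in 10.6 is safety and tolerability. Objective 3 is to "Assess pre- and post-treatment pain metrics and change in upper extremity circumference and induration". Sections 18.3 and 23.1 list the expected side effects, including dizziness, headache, nausea and shortness of breath. Section 23.2 lists those four again as adverse events, with no condition on when they began. Under 23.6 the safety committee decides on the incidence of side effects, adverse events and serious adverse events. Section 11.3 confirms that there is one group.

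**The concern.** A symptom reported after treatment can be called treatment-emergent only if its state before treatment is known. In a single-group study no control arm supplies the background rate, so the patient's own reading earlier in the visit is the only comparator. For the four general symptoms that reading is not described. For pain and swelling it exists, but no rule says that it will be used to decide what counts as a device effect. Section 10.5 itself notes that "Lymphedema in and of itself can be uncomfortable, if not downright painful".

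At stake is the main safety summary. If symptoms brought to the clinic are recorded as device effects, the incidence is too high. If staff or patients put a real effect down to the disease or to how the patient felt on arrival, it is too low. The same gap carries into step 7: a headache present on arrival could be recorded against both the device and standard care. A missed pre-device reading cannot be recovered afterwards.

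**Working it through.** The plan gives no figure for this point, so there is none to reproduce. The check has two parts.

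**1. What is read, and when (18.1, 18.3, 10.4, 10.6, 23.2)**

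| Symptom | Before device (step 3) | After device (step 5) | Onset rule in 23.2 |
|---|---|---|---|
| Pain, discomfort | Survey section; objective 3 plans a pre/post comparison | Survey section and side-effect question | None; the only qualifier is whether removing the device relieves it |
| Swelling | Circumference and induration at six points | Both repeated, and side-effect question | As above |
| Headache, dizziness, nausea, shortness of breath | None described | Side-effect question | None |

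Step 3 therefore does not deliver what 10.4 describes for side effects, and no row has a rule for a symptom already present on arrival.

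**2. Scale, under an assumption**

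Inputs from the documents: 15 subjects (11.2, 23.6) and 4 weekly visits each (18.1 step 8, 18.4), so 15 × 4 = 60 sessions. The first review cohort is 5 subjects (23.6), so 5 × 4 = 20 sessions.

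Input not in the documents: p, the chance that a patient arrives with at least one of the four symptoms. I take 1%, 2% and 5% as an illustrative range.

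- Expected affected sessions: 60p.
- Chance of at least one, sessions independent: 1 − (1 − p)^60 for the study, 1 − (1 − p)^20 for the first cohort.
- Chance of at least one, symptoms fully clustered (a patient has the symptom at every visit or at none): 1 − (1 − p)^15 for the study, 1 − (1 − p)^5 for the first cohort.

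| p | Expected sessions of 60 | Study, independent | Study, clustered | First cohort, independent | First cohort, clustered |
|---|---|---|---|---|---|
| 1% | 0.6 | 45% | 14% | 18% | 5% |
| 2% | 1.2 | 70% | 26% | 33% | 10% |
| 5% | 3.0 | 95% | 54% | 64% | 23% |

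For example, at p = 2%: 1 − 0.98^60 = 0.702 and 1 − 0.98^15 = 0.261. Recurrent symptoms tend to cluster within patients, so the truth should lie between the two columns.

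These are chances that a symptom is present on arrival. They equal the chance of misattribution to the device only if every such symptom is then recorded as a device effect, so for a given p they are upper bounds on that error. They do not measure the opposite error, a real effect dismissed as pre-existing.

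**The case against.** The strongest reply is that the plan does take a symptom baseline. The survey in step 3 is one, it is repeated after the device, and swelling is measured at six points before and after. That stands. A reader might infer from the late side-effect question that no symptom has a pre-device reading, and for pain and swelling the documents contradict this.

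Second, a reader might infer that symptoms present on arrival are counted as device effects. No section says so. Step 5 asks what patients experienced, which many would answer for new symptoms only, and 23.3 says participants are watched closely during data collection, so onset may be noticed. This also stands: the classification is unspecified, not wrong by rule.

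Third, the survey items and the data collection tool are attachments outside the text. Either might cover headache or nausea before the device, and 10.4 suggests that a pre-device check may have been intended. This cannot be checked. If a check exists, 18.1 should state it, because 18.1 is what staff follow.

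Fourth, the link to suspension is uncertain. Section 23.6 says: "For occurrence of any unanticipated side effects or adverse events, the study will be immediately suspended". The word for unanticipated may govern both nouns. The four symptoms are anticipated risks in 23.1 and also adverse events in 23.2, so the text does not settle whether a listed headache would suspend the study. The point here does not depend on that, because the committee reviews the incidence on either reading.

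**Conclusion.** The point holds for the four general symptoms: the procedures describe no pre-device check, and the lay description does not match them. It also holds, for every symptom, that no rule classifies what was present on arrival. The side-effect incidence that serves objective 2 and the safety committee therefore cannot separate device-emergent from background symptoms.

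It would be tempting to add that the bias always runs against the device. The documents do not support that, since without a recorded baseline a true effect can be dismissed as easily as a background symptom can be blamed on the device.

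The size is not known. The illustrative chance of at least one affected session in the study runs from 14% (p = 1%, full clustering) to 95% (p = 5%, independence). It rests entirely on the assumed p and the assumed dependence between visits. This is a worthwhile, inexpensive improvement to the safety data, not a flaw that invalidates the study.

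**What to change.** - Reconcile 10.4 with 18.1 steps 3 and 5. Ask the step 5 symptom list in step 3, before the sleeve goes on, in the same words. If the data collection tool already does this, say so in 18.1.
- For each symptom after the device, record whether it is new, worse or unchanged from that visit's pre-device reading. Use the existing survey and arm measurements in the same way for pain and swelling.
- Give the safety committee every symptom with both readings. Base the device side-effect incidence on new or worse symptoms, and show the all-symptom count beside it. The flag describes an event; it does not remove one from safety reporting.
- Leave the suspension rule in 23.6 as it stands; this change neither needs nor proposes any alteration to it.

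The cost is about one minute per visit and one extra analysis flag, with no added staff. The time is tight but available: the stated 3 + 36 + 3 = 42 minutes of measurement and treatment leave 45 − 42 = 3 minutes for fitting and this checklist.
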